Joint Labor-Management Health and Welfare Funds offer a unique opportunity to study workplace interventions. Unionized construction workers are typically covered by Taft-Hartley Health and Welfare Funds, which administer health insurance plans that cover approximately nine million U.S. adults.³⁸ These union health funds are coordinated by national unions, governed by joint labor-management boards at a regional or national level, and are funded by contributions from employers (contractors) and by the union members. These funds offer several advantages to study implementation of employment related guidelines. First, these funds cover a large proportion of the employed population at highest risk for opioid overdose. Second, eligibility for health benefits is linked to hours worked by each covered member, so data on both individual work hours and health care expenditures are available across multiple employers, allowing linkage of diagnoses and treatment to employment outcomes, regardless of change in employer by the member. Third, interventions to reduce tobacco use have been conducted across multiple Taft-Hartley plans,^{38, 39} indicating the potential for conducting opioid policy intervention studies in a similar manner. As described below, our nationally recognized team of occupational health and addiction researchers has worked extensively with our local construction unions and health funds to analyze health claims and work hour data and to implement workplace health interventions. The structure of these union health funds and our strong working relationships with partner organizations support the feasibility of our proposal to obtain data and influence workplace health policies in this group.

In summary, there is an urgent need to develop and test the effectiveness of best practices employment policies and employment-linked health insurance plans in order to reduce OUD and

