9.3 POPULATIONS FOR ANALYSES

We will calculate descriptive statistics for the full population of the administrative data. The data will include active and retired members from the benefits-eligible group of the period May 2019-May 2022. We will include any member who was continuously benefits-eligible but censor them after they drop eligibility or don't self-pay to continue coverage. All retired members who self-pay will also be included in the analyses.

We will calculate descriptive statistics for those members who complete the worker survey. We will compare the demographics (age, gender, race) of those who completed the survey to the union

membership to see if the two groups (surveyed versus union members) have similar characteristics. This will help assess the feasibility of the survey recruitment methods to obtain a representative sample.

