9.4 STATISTICAL ANALYSES

9.4.1 GENERAL APPROACH

Outcome data is derived from the administrative claims and worker surveys.

Administrative claims will be collected over two periods (06/01/2019-05/31/22) and (06/01/2022-05/31/2023). All three outcomes of interest are primary outcomes. The analysis will examine the group level change of the outcome, adjusting for length of time in each period, to show a reduction in impaired health or behaviors that may be due to implementation of the intervention.

Worker surveys will be collected by member worker surveys from each health fund at two points in time. The baseline, before implementation of the intervention, and at 6-months after start of implementation. All members will be invited to complete a survey. The desired sample is 300 surveys per health fund at each time point. The outcomes are composed of one or more items in the surveys. Group level statistics will be computed as the proportion of members with a positive response to each outcome. The change in proportion by time point may be due to implementation of the intervention.

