93. *The Family and Medical Leave Act of 1993: Leave for Treatment of Substance Abuse*. 1993 [cited 2021 September 23]; Available from: <https://www.law.cornell.edu/cfr/text/29/825.119>.

94. Substance Abuse and Mental Health Services Administration. *Plan and Implement a Program*. 2020 [cited 2021 October 14]; Available from: <https://www.samhsa.gov/workplace/toolkit/plan-implement-program>.

95. Substance Abuse and Mental Health Services Administration. *Tip 63: Medications for Opioid Use Disorder*. 2018 2021 [cited 2021 October 13]; Available from: https://store.samhsa.gov/sites/default/files/SAMHSA_Digital_Download/PEP21-02-01-002.pdf.

96. Howard, J., et al., *Medication-Assisted Treatment for Opioid Use Disorder*. Workplace Solutions, 2019.

E. Monthly Health Fund meeting script_followup

Monthly Health Fund follow-up meeting:

Date: _____

Organization: _____

Participant: _____

Notes from past Interview:	
1. Are you in the process of making any changes to your opioid prevention program? If yes please describe (date of adoption,	

implementations strategies, how are you measuring effectiveness of the change, participation rates in programs for workers, adherence to and enforcement of policies, and methods for disseminating programs)
 
a. Have you made any changes to existing opioid prevention programming? If so please explain
	

2. Did you review the guidelines? If yes, what did you find useful and what do you think is missing from the guidelines?
 
a. Did you complete the needs assessment?b. Did you follow the process guide, steps 1, 2, and 3?c. What did you list on your inventory of resources?d. Did you make a plan?	

3. What are challenges or barriers are you encountering in trying to implement your program?
	

G. Data management of Administrative Health Claims and Worker Surveys
Data management of Administrative Health Claims and Worker Surveys

a) Administrative Health Claims

a. Inclusion

- i. Health plan member (as opposed to dependent or retired) at some point during study period (6/1/2019-5/31/2022), per census records
 - 1. Could transition to retired status during study period, but needed to start as member

b. Exclusion

- i. Missing eligibility or termination dates in census records
- ii. Cancer diagnosis
 - 1. Ever received ICD-10 code in medical claims data: C00.x–C26.x, C30.x–C34.x, C37.x–C41.x, C43.x, C45.x–C58.x, C60.x–C76.x, C77.x–C85.x, C88.x, C90.x–C97.x)

c. Initial work

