- i. Medical claims (“claims”), pharmacy claims (“fills”), census data was received “piecemeal”
 - 1. By timeframe (i.e, quarterly) and type (plan member, dependent, retired)

- ii. Consolidate files into single datasets for claims, fills, census data and work histories
- iii. Create eligible/valids file—this is the list of members eligible for the study, based on above criteria
- iv. Limit all analysis data (claims, fills) to members in the eligible/valids list
- d. Opioid/claim linkage: The process of linking opioid prescriptions (from pharmacy fills) to diagnoses (from medical claims) involves two main steps: 1) assign opioid fills to claims based on timing and acuity, and 2) assign opioid refills to claims
 - i. Opioid/claim join using timing and acuity
 - 1. Create file of opioid fills from pharmacy fills data, using CDC file ["CDC opioid NDC_oral MME conversion_update_2020.xlsx"] to identify opioids
 - 2. Split opioid claims into two groups based on refill status: initial fills and refills (note this is using refill status indicated by the health fund. Many members have serial initial fills and not refills in these data; those would be in the initial fills file)
 - 3. Assign diagnosis category for each claim, using ICD-10 and procedure codes. Categories include “MSD surgery”, “Acute MSD injury”, “Chronic MSD”, and “Other diagnosis”
 - a. If more than one diagnosis category is present on a single claim, assign claim to the highest acuity (MSD Surgery, then Acute MSD Injury, then Chronic MSD, then Other diagnosis)
 - 4. Join claims with initial fills by member ID (UID)—this generates a many-to-many match
 - 5. Calculate time difference between claim date and fill date
 - a. If fill<before claim, use this information to generate opioid naïvety status for each claim
 - 6. If fill is 0-3 days after claim and the claim diagnosis category is not “Chronic MSD”, assign the opioid to the claim. If more than one claim fits the criteria, assign based on order other diagnoses, then MSD surgeries, lastly acute MSD injuries. If more than one claim is still eligible, use the smallest time difference between claim and fill to assign the fill
 - 7. Among the unlinked opioid fills, if fill is 0-30 days after a chronic MSD claim, assign opioid to that claim. If more than one claim meets the criteria, assign based on time difference (i.e., smallest time difference between claim and fill date)
 - ii. Assign opioid refills to claims

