 5. Indicator variable for total days supply in a cycle > 60 for any given cycle
 - viii. Multiple Rx in a single visit: multiple Rx filled on the same day and NPI is the same between fills

- ix. Multiple Rx on same day, different provider: multiple Rx filled on the same day and NPI between Rx different. Could indicate doctor shopping
- x. Misuse: “Overlapping Rx” OR “Multiple Rx on same day, different provider”
- f. Diagnoses. These variables were generated from information in the medical (i.e diagnosis and procedure) claims. Diagnoses are assessed at the claim level, and “rolled up” to the worker (i.e, has worker ever had a diagnosis for X)
 - i. MSD surgery: CPT codes 20005-21010; 21500-22900; 62263-63746; 64400-64999
 - ii. Acute MSD injury: ICD-10 codes ranging S00-T14
 - iii. Chronic MSD: ICD-10 codes M.x, G54-G57
 - iv. Recurring acute injury. Acute MSD injuries that occur across multiple claims are recoded as “recurring injuries”. These are combined with chronic MSD for our purposes
 - 1. ICD-10 codes for acute MSD injuries are identified on a given claim (see above)
 - 2. If the same ICD-10 code occurred on a previous claim more than 30 days before the claim in question, the acute MSD injury is recoded as “recurring injury” on the claim in question and will no longer be counted as an acute MSD injury
 - 3. Using this method, the first occurrence of a given acute MSD injury ICD10 code will be left as “acute MSD injury”
 - v. Other diagnosis: Claims that do not fit into i-iv above are coded as “other Dx”
 - vi. Acuity: claims can have multiple diagnoses associated with them. Acuity is assigned as follows, regardless of other diagnoses associated with the claim: MSD surgery, Acute MSD Injury, recurring injury or chronic MSD, other diagnoses.
 - 1. So if a claim had codes for both MSD surgery and chronic MSD, the acuity is assigned to MSD surgery
- g. Description of the study sample [all data are in “claims eligibility_20230213.docx”, unless otherwise noted]
 - i. Demographics and worker characteristics
 - 1. Gender
 - 2. Age in 2022
 - 3. Plan status (Active, COBRA, etc)
 - 4. Time worker eligible for benefits during study period
 - 5. Gaps in eligibility
 - ii. Plan utilization
 - 1. Proportion of workers with a health claim, pharmacy claim, overlap of these
 - iii. Distribution of diagnoses based on original order of acuity
 - iv. Diagnoses. Number of workers with:
 - 1. MSD surgery
 - 2. Acute MSD injury

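### The claims comparison has no eligible-time denominator and no settled follow-up population, so the reported change is biased in a direction the plan leaves open

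*Combined protocol and SAP*

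**What the plan says.** Section 9.4.1 sets the two periods: "Administrative claims will be collected over two periods (06/01/2019-05/31/22) and (06/01/2022-05/31/2023". That is 36 months against 12. The only adjustment named is "The analysis will examine the group level change of the outcome, adjusting for length of time in each period", with no method attached. Section 9.4.2 a) reports categorical outcomes as N (%) and compares baseline with follow-up by Fisher's exact test.

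The population is described in three places.

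- **Section 9.3:** "The data will include active and retired members from the benefits-eligible group of the period May 2019-May 2022". It adds: "We will include any member who was continuously benefits-eligible but censor them after they drop eligibility or don't self-pay to continue coverage".
- **Data-management appendix (Section 10.2):** a member is included if on the plan "at some point during study period (6/1/2019-5/31/2022), per census records". The instruction that follows is: "Limit all analysis data (claims, fills) to members in the eligible/valids list". Members with missing eligibility or termination dates are excluded, so those dates are expected to be available.
- **Sections 5 and 5.1:** benefits-eligible members from May 2019 to May 2023.

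The appendix also lists "Time worker eligible for benefits during study period" and gaps in eligibility, but only under the description of the sample. Section 2.2 notes that "eligibility for health benefits is linked to hours worked by each covered member" and that construction work is often intermittent, so partial coverage is to be expected.

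**The concern.** Every claims outcome is built from medical claims and pharmacy fills, which exist only for days of coverage. A member covered for four of the 36 baseline months can be flagged only in those four. A member whose coverage ended in 2020 cannot be flagged at all in follow-up. Neither a percentage of listed members nor Fisher's exact test uses an exposure time or a censoring date, and scaling by period length does not supply one.

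The two periods are also filled differently. Under the appendix rule, people who joined during baseline are on the list, while people who joined after 5/31/2022 are not. Leavers are therefore replaced in baseline but not in follow-up. This problem is separate from 36 months against 12, and it remains after the period lengths are adjusted for exactly.

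Two things are at stake. Section 9.4.1 describes the analysis as showing a reduction that may be due to the intervention, so an artefact in either direction could be misread. Sections 9.1 and 9.2 say the data will feed the power calculation of a future trial, so biased rates would carry forward.

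**Working it through.** **The plan's own figure.** Section 9.2 expects 3 x 10,200 = 30,600 members, which reproduces. The protocol summary gives 33,300, which is (33,300 - 30,600)/30,600 = 8.8% higher. The documents give no turnover, event rate or persistence of conditions.

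**Assumptions.** Each fund keeps a stable size N. Members leave at rate t a year, are replaced, and do not return. The event rate while eligible is constant and there is no true change. Turnover t is taken as 5, 10, 20 and 30%.

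**Step 1: appendix list as the denominator in both periods.**

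- List size = N + 3tN = N(1 + 3t).
- Baseline eligible years = 3N, so the share of list time actually observed = 3N / [3N(1 + 3t)] = 1/(1 + 3t).
- Follow-up eligible years on the list, with no joiners = N(1 - e^-t)/t, so the observed share = [(1 - e^-t)/t] / (1 + 3t).
- Follow-up/baseline ratio = (1 - e^-t)/t.

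At t = 20%: 1/1.6 = 0.625; (1 - e^-0.2)/0.2 = 0.906; 0.906/1.6 = 0.57.

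| t | Listed, not covered at start of follow-up, 3t/(1+3t) | Baseline share | Follow-up share | Ratio | False fall |
|---|---|---|---|---|---|
| 5% | 13% | 0.87 | 0.85 | 0.975 | 2.5% |
| 10% | 23% | 0.77 | 0.73 | 0.952 | 4.8% |
| 20% | 38% | 0.63 | 0.57 | 0.906 | 9.4% |
| 30% | 47% | 0.53 | 0.45 | 0.864 | 13.6% |

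Rates per year are therefore 13-47% too low in baseline and 15-55% too low in follow-up.

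**Step 2: count each worker once per period, as N (%) does.** Assume a rate r = 3% per eligible year. A member eligible at the start of a window of T years is flagged before leaving with probability p(T) = [r/(r + t)][1 - e^-(r+t)T]. Workers flagged in baseline = N[p(3) + t x integral of p(3 - s) over s from 0 to 3]. Workers flagged in follow-up without joiners = N p(1). With joiners, the matching integral over one year is added. The table gives the follow-up proportion per year divided by the baseline proportion per year, with no true change.

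| Denominator | t = 0 | 5% | 10% | 20% | 30% |
|---|---|---|---|---|---|
| Appendix list, both periods | 1.03 | 1.00 | 0.98 | 0.93 | 0.88 |
| Leavers dropped from follow-up only | 1.03 | 1.15 | 1.27 | 1.48 | 1.67 |
| Ever-members of each period | 1.03 | 1.13 | 1.21 | 1.36 | 1.49 |
| Eligible member-time | 1.03 | 1.03 | 1.03 | 1.02 | 1.02 |

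The 1.03 at zero turnover comes from counting a worker once over a longer baseline: (1 - e^-0.03) / [(1 - e^-0.09)/3] = 1.03. Relative to that value, the first row shows about the same fall as Step 1. Relative to 1.00 the fall is smaller, and it is absent at 5% turnover. The second and third rows rise because baseline ever-members are observed for only part of their 36 months.

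**Step 3: persistent conditions.** Suppose 1% of members are persistent cases and 1% a year are new. With no turnover, baseline is (1% + 3 x 1%)/3 = 1.33% a year and follow-up is 1% + 1% = 2%, a ratio of 1.5. Eligible time is then complete in both periods, so a member-time denominator leaves the ratio at 1.5. Twelve-month baseline windows give 2% each and a ratio of 1.0. On the same assumption, with the appendix list in both periods, the ratio is about 1.4-1.5 at 5% turnover and 1.15 at 30%.

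**The case against.** A reader might infer that the plan scales by calendar length, keeps leavers in the follow-up denominator and so has a false reduction built in. The documents do not support that reading.

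- The word calendar is not in Section 9.4.1. Length of time could mean each member's own time, and the appendix does derive eligible time and gaps.
- Section 9.3 intends leavers to be censored, and a percentage can simply leave out members censored before 6/1/2022.
- Sections 5 and 5.1 run to May 2023, so the baseline-only list is not the only population statement. The appendix cites a file whose name carries the date 20230213, before follow-up closed, and may describe the baseline extract only.
- The sign of the bias depends on the denominator and on persistence. Steps 2 and 3 show rises as readily as falls.

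All of this stands, and it rules out claiming one direction. It does not rescue the comparison. Sections 9.4.1 and 9.4.2 never apply the censoring, and the specified summary and test cannot use a censoring date. Leaving leavers out of follow-up alone replaces a fall with a larger rise. Censoring also does nothing for late entry, and continuous eligibility in Section 9.3 conflicts with eligibility at some point in the appendix.

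It is also fair that the trial is a feasibility study, with no comparator, no powering and, by Section 9.1, no formal hypothesis testing. That limits the harm to description and planning.

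**Conclusion.** The concern holds in this form: the claims comparison lacks an eligible-time denominator, the Section 9.3 censoring is not put into operation, and the follow-up population is not consistently defined. With no true change, the reported change is biased. The bias is a fall of about 2.5-14% if the appendix list serves both periods, and smaller against 1.00 when each worker is counted once. It is a rise, with ratios of about 1.15-1.67, if leavers are dropped from follow-up only, and of about 1.13-1.49 if ever-members of each period are used. Baseline rates per year over ever-members are understated by about 13-47%.

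These sizes rest on the assumed 5-30% annual turnover, a stable fund and a constant event rate. The once-per-period ratios also assume 3% per eligible year. Persistent conditions could outweigh the fall. No confirmatory conclusion is at risk. What suffers is the descriptive change and the rates passed to the next trial's power calculation.

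**What to change.** 1. In Sections 9.4.1 and 9.4.2 a), replace the adjustment for period length with a denominator of benefits-eligible member-time within each period, taken from the census eligibility and termination dates. Apply the Section 9.3 censoring, start late joiners at their entry date, and let a member with no eligible day in a period contribute nothing to it.
2. Report workers flagged per 1,000 eligible member-years beside N (%). If a model is used, enter log eligible time as the offset.
3. Give the baseline also in 12-month windows. Member-time alone does not make a persistent condition, counted once per period, comparable over 36 and 12 months.
4. Reconcile the population windows in Sections 5, 5.1 and 9.3 and the data-management appendix, so that members joining after 5/31/2022 enter follow-up.

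The cost is wording and a few lines of code, because the dates are already required and eligible time is already derived. The small downside is that results appear as rates as well as simple percentages.

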Guidelines can help prevent new cases of opioid misuse and OUD. Recent CDC guidelines recommend limiting initial prescriptions of opioids for acute pain, and limiting the prescription of opioids for treatment of chronic non-cancer pain, in order to reduce future opioid misuse and OUD.¹⁹ These recommendations are supported by analyses of state level Medicaid data and state level workers' compensation data.²⁰⁻²² Positive evidence directly relevant to workers comes from the implementation of guidelines in Washington State that limited opioid prescriptions beyond the acute period for work-related injuries.²³ Prior authorization requirements, with hard stops to prescription approval, resulted in a large and sustained drop in persistent opioid use and a reversal of lost work patterns related to opioid prescribing seen in the prior decade. Similar success was seen in Texas, where requirements for pre-authorization for many opioid medications led to a marked decrease in prescribing.²⁴ Several states have now taken steps to address opioid use in their workers' compensation systems by limiting opioid availability, educating health care providers on responsible opioid prescribing, and increasing awareness of the risks of OUD among injured workers.^{25, 26} While some state-level plans have implemented these policies, most commercial insurance programs and health funds have not and this remains a significant gap.^{27, 28} Most of opioid prescribing recommendations are written from a clinical or statewide insurer perspective and do not consider the influence that employers can have with prevention and support of chronic opioid use and misuse. There is increasing consensus that PBMs and employer based health funds also have an important role to play in improving health and limiting disability among their workforce by limiting the use of opioid medications for their employees, and by managing opioid use and claims more actively.²⁹ The challenges presented to employers about what to do regarding opioid use in the workplace and the role that practical guidelines can play motivates Aim 1 of this proposal. In **Aim 1**, we will identify best practice healthcare and employment policies regarding opioid use and misuse.

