2.3.2 KNOWN POTENTIAL BENEFITS

Unions, employers, and health funds will gain greater awareness of the opioid epidemic and how they can address it in their workforce using the Workplace Opioid Guidelines that will be created in this project. Workers will learn of the risks of opioid use and be made aware of workplace programs and policies related to opioid use and treatment. Health claims, pharmacy data, and work hours data are important for showing the improvement in health (changes in number of opioid prescriptions, and number of workers with opioid use disorder) and employment outcomes (change in lost work hours/days in work hour records) after the Health Fund adopts policies and programs from the guidelines. These changes will help determine the effectiveness of these guidelines.

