3 OBJECTIVES AND ENDPOINTS

The objective of this trial is to evaluate the feasibility of implementing the workplace opioid guidelines in union health funds of the construction trades and measure the implementation and effectiveness of changes made to the union health fund policies, programs, and benefits made in response to using the workplace guidelines. We will assess implementation using process measures recorded over a 6-month period of time using the REAIM framework. We will assess effectiveness by measuring changes in the administrative claims and from worker surveys collected from members.

The primary outcomes will show a change in a) the proportion of workers with opioid misuse, opioid use disorder and opioid overdose collected from administrative data over a 4 year period (3-years prior to the intervention, and one-year of the intervention implementation) and b) the proportion of workers with opioid misuse measured from worker surveys from each of the union health funds over a 6-month period after start of implementation of the intervention.

The secondary outcomes will show a change in a) the proportion of workers with lost time measures and b) the proportion of workers willing to seek help measured from worker surveys from each of the union health funds, and collected over a 6-month period after start of the implementation of the intervention.

The feasibility trial will be deemed successful if the study successfully recruits three union health funds, and collects measures to assess the implementation of the intervention and effectiveness of health and behaviors during the trial period. This is not a randomized trial, nor is the study powered to expect statistical changes in the outcome measures. The benefit for conducting the feasibility trial is to test all procedures in the specific population to guide plans for a future randomized trial.

OBJECTIVES	ENDPOINTS	JUSTIFICATION FOR ENDPOINTS
Primary		

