9.4.2 ANALYSIS OF THE PRIMARY ENDPOINT(S)

- a) Administrative Claims
 - a. Outcome variables of interest
 - i. Opioid misuse- “Overlapping Rx” OR “Multiple Rx on same day, different provider”
 - ii. Chronic opioid use- more than 60 days supply in a 90 day window
 - iii. Opioid use disorder- ICD-10 T40* (Poisoning by, adverse effect of and underdosing of narcotics and psychodysleptics) &/Or ICD-10 F11* (opioid related disorders) &/or prescribed MAT (Drug name contained “methadone” or “buprenorphine”; picks up buprenorphine, suboxone, zubsolv, naltrexone, methadone, narcan, and vivitrol)
 - b. Compute statistics for baseline period (06/01/2019-05/31/2022) and follow-up (06/01/2022-05/31-2023)

- i. Categorical data will be presented as N (%), continuous data as median (25th, 75th %tile)
- c. Run comparisons between baseline and follow-up time points
 - i. Comparisons involving two categorical variables will be made using Fisher's exact test
 - ii. Comparisons involving a continuous variable and a categorical variable will be made using Wilcoxon Rank Sum test or Kruskal Wallis test

b) Worker Survey

- a. Outcome variable of interest
 - i. Opioid misuse- Participant responded yes to one of the following two questions:
 - 1. Did you use the pain medication more than prescribed, or for a longer period than prescribed? [pnmed_longer]x
 - 2. Have you used prescription pain medications that were prescribed to someone else? [pnmed_othersrx]x
 - b. Compute the change at 6 months post-intervention (change of opioid misusep) of group-level data collected from groups of health

All endpoints are independent outcomes.

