9.4.8 TABULATION OF INDIVIDUAL PARTICIPANT DATA

Administrative claims data will be combined using a unique linking variable. The claims data will include the date of service in order to identify the time point. Three years of data will be collected at baseline (May 2019-May 2022) and one year of data for follow up (June 2022-May 2023). The data will be analyzed as group level data by time point.

The worker surveys will be analyzed as group level data by time point. The data will not be tabulated by individual participants, nor will the administrative data be linked to the worker survey data.

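### The claims endpoints set one 36-month block against one 12-month block, so any background trend in opioid use, falling or rising, is mixed into the change used to assess effectiveness

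*Combined protocol and SAP*

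**What the plan says.** Section 9.4.1 divides the claims into 06/01/2019 to 05/31/2022 and 06/01/2022 to 05/31/2023. The group-level change is examined "adjusting for length of time in each period", and its stated purpose is "to show a reduction in impaired health or behaviors that may be due to implementation of the intervention". Section 9.4.2 repeats the two blocks, summarises categorical outcomes as N (%), and compares them with Fisher's exact test.

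Section 9.4.8 says "The claims data will include the date of service in order to identify the time point". The date thus serves only to place a record in one block or the other. Section 4.2 states that no comparator was needed, and Section 9.4.9 plans no exploratory analyses.

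The change is also given an evaluative role. Section 3 says "We will assess effectiveness by measuring changes in the administrative claims and from worker surveys collected from members", and Section 2.3.2, after describing claims, pharmacy and work-hours data, says "These changes will help determine the effectiveness of these guidelines".

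**The concern.** Adjusting for period length puts three years and one year on the same exposure scale. It does nothing about calendar time. If opioid misuse, chronic use or coded opioid use disorder (OUD) was already moving in these funds before June 2022, that movement appears in the before-after difference, and nothing else in the plan would reveal it.

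Two uses of the result are exposed. One is the reading of a primary endpoint as evidence about the guidelines. The other is planning of the future trial: Sections 9.1 and 9.2 say the data will inform its power calculation, and a two-period change containing a trend would be a poor effect size to plan on.

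**Working it through.** **Inputs from the documents.** Baseline runs 36 months and follow-up 12 months (Section 9.4.1). The midpoints are about 1 December 2020 and 1 December 2022, 24 months apart. Section 9.2 gives 3 funds × 10,200 members = 30,600, which reproduces exactly. No effect size, alpha or event rate is stated, so there is no power figure to reproduce.

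**Assumptions, not in the documents.** A constant relative change of d a year; a baseline prevalence of 3% (1% as a second case); independent members; no intervention effect. "Adjusting for length" is taken to mean comparing yearly rates.

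**Step 1: apparent change under no effect.** With year 1 set to 1, the baseline average is [1 + (1−d) + (1−d)²]/3, the follow-up year is (1−d)³, and R is follow-up divided by baseline.

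**Step 2: two-sample z.** With p₀ = 0.03, p₁ = 0.03 × R and p̄ their mean, z = (p₀ − p₁)/√[p̄(1−p̄) × 2/30,600].

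| Decline per year | Baseline average | Follow-up | R | Apparent reduction | p₁ | z | p |
|---|---|---|---|---|---|---|---|
| 3% | 0.970 | 0.913 | 0.941 | 6% | 2.82% | 1.3 | 0.19 |
| 5% | 0.951 | 0.857 | 0.902 | 10% | 2.71% | 2.2 | 0.03 |
| 10% | 0.903 | 0.729 | 0.807 | 19% | 2.42% | 4.4 | 0.00001 |

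For the 5% row: p₀ − p₁ = 0.00295, standard error = 0.00135, ratio 2.2. At 1% prevalence the same 5% decline gives z = 1.25 (p = 0.21), so whether the comparison looks convincing depends heavily on both assumed values.

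**Step 3: the other direction.** A rise of 5% a year gives 1.158/1.051 = 1.10, an apparent 10% increase with no effect. A true reduction of about that size would be hidden.

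**Step 4: can dated data remove it?** Forty-eight monthly Poisson counts were simulated (1,000 sets per scenario; yearly rates of 1%, 2% and 5%; declines of 0%, 3%, 5% and 10%). At a 2% rate and a 5% decline, the plain before-after model gave a mean rate ratio of 0.90 and reached p < 0.05 in 54% of sets. With a linear calendar-time term the figures were 1.00 and 4.9%. Over all scenarios the trend-adjusted ratio was 0.99 to 1.00, with 4.4% to 6.1% false positives.

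The price is precision. At a 2% rate with no trend, the before-after standard error of the log ratio is √(1/1,836 + 1/612) = 0.047 (612 = 30,600 × 0.02; 1,836 = 3 × 612). With the trend term it was 0.071, about half as large again.

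This simulation uses a common start date and a trend that really is log-linear. It shows the principle and does not validate a particular model for these three funds.

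**The case against.** The strongest reply is that this is a three-fund feasibility study. Section 3 defines success as recruiting funds and collecting measures, and says the study is not powered to detect change. Section 9.1 disclaims formal hypothesis testing, and the attribution in Section 9.4.1 is hedged. That stands as a reason not to demand a segmented model as the primary analysis. It does not remove the point, because Sections 2.3.2 and 3 still use the change to judge effectiveness and Section 9.4.2 still lists tests.

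A reader might infer from Section 2.2 ("Several states have now taken steps to address opioid use") that prescribing limits were already spreading through this population. The documents do not support that. The sentence concerns workers' compensation systems, and the next one says most commercial programs and health funds had not adopted such policies. Nor can one say that the claims result would show a reduction under no effect: no trend for these funds is given, and direction may differ by outcome. OUD, for instance, counts poisoning codes and treatment fills. A reader might also infer that the future trial's effect size will be inflated. The plan says only that the data will inform power, not that the observed change will be the planning effect.

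Two technical objections stand:

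- The method of length adjustment is not given. If members were instead counted once per block with no annualising, a constant 1% to 5% yearly rate with independent years would look like a drop of about 65% with no trend at all (at 1%: 1 − 0.99³ = 2.97%, and 1/2.97 − 1 = −66%). The ratios above would not then describe the statistic.
- The data-management attachment in Section 10.2 defines OUD as ever coded or ever on medication-assisted treatment, and builds chronic use from 90-day cycles starting at each worker's first fill. Neither can be tabulated by calendar quarter as written.

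**Conclusion.** The point holds in conditional form. The planned two-block contrast cannot separate the intervention from background change over roughly two years, and the plan contains no other analysis that would. How much this matters is unknown from the documents: about 6%, 10% or 19% apparent reduction for assumed declines of 3%, 5% or 10% a year, and a masked benefit if the trend was upward. The z values of 1.3, 2.2 and 4.4 rest further on 3% prevalence and independence. Independence is doubtful, since largely the same members appear in both periods.

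It is worth correcting because the remedy uses data already requested. In a feasibility study without formal testing, the remedy belongs beside the two-period description as support.

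**What to change.** 1. Using service and fill dates, report each claims outcome by quarter (or year) and by fund, with members eligible in that interval as denominator. The attachment already excludes members lacking eligibility or termination dates, so denominators can be built.
2. Define the outcomes for an interval: OUD as dated events or period prevalence rather than ever; chronic use with a rule assigning 90-day cycles to calendar intervals. State how period length is adjusted in the two-period figures.
3. Keep the two-period figures as description. Beside them, as a supportive analysis, estimate the change at each fund's actual intervention start relative to its baseline trend, with a confidence interval. Fund-specific dates matter because Section 6.1.2 starts the intervention only after baseline collection and the guideline file is dated 07062022, so 1 June 2022 may count pre-intervention time as follow-up.
4. State that the unadjusted two-period change will not be attributed to the intervention or used as the effect size for the R01 power calculation.

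Costs: redefinition and programming, and a wider interval, perhaps with fewer than four usable follow-up quarters in a late-starting fund. The estimate also relies on the baseline trend continuing, and that baseline spans the 2020 pandemic period. State this reliance and check it by sensitivity analysis, for example by leaving out the 2020 quarters or varying the trend's form.
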